- ICU length of stay (LOS)
- Hospital LOS
- End organ failure (measured by BUN, creatinine, and liver function tests)

The secondary study endpoints are to evaluate whether NO delivered through the neonatal CPB circuit can decrease various biochemical markers of ischemia/reperfusion injury and oxidative damage. Markers to be analyzed will include:

- cardiac troponin I
- N-terminal prohormone for brain natriuretic peptide (NT-proBNP)
- plasma malondialdehyde (MDA) levels
- superoxide dismutase
- interleukins (IL)
- lactate dehydrogenase (LDH)
- procalcitonin
- tumor necrosis factor (TNF alpha)
- C-reactive protein (CRP)
- Creatine phosphokinase-MB (CPK-MB)

The primary safety measure is the level of methemoglobin while NO is being administered during cardiopulmonary bypass. The level will be checked every

½ hour per standard clinical practice, and NO administration will be adjusted accordingly, to keep the methemoglobin level below 3%.

10) Procedures Involved

Design

The study will employ a double-blind placebo-controlled randomized block design.

Sample

Twenty-four neonates with HLHS or its variants requiring surgical repair in the first few days of life will be randomized into 2 groups.

Group 1 will include 12 subjects who will receive inhaled NO via the CPB circuit for the duration of surgery. Group 2 will include 12 control subjects. These controls will receive an identical NO via CPB set-up, but will not receive NO during surgery. The subjects in both groups will undergo the standard Norwood procedure with a central systemic to pulmonary shunt or right ventricle to pulmonary artery shunt (Sano shunt). The only difference between groups will be the administration of NO via CPB.

Standard Intra-operative protocol:

After induction of general anesthesia using opiates (Fentanyl) and muscle relaxant, appropriate arterial line and central venous line access will be obtained. Intra-operative monitoring of arterial blood pressure, central venous pressure, systemic oxygen saturation, cerebral and somatic (kidney) near-infrared spectroscopy, will be done throughout surgery.

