After adequate positioning, a regular median sternotomy incision will be done. The thymus gland is resected for better exposure. Under full heparinization (activated clotting time >300 sec), CPB is instituted using an arterial cannula inserted in the ascending aorta (or ductus arteriosus in patients with HLHS), and a venous cannula inserted in the right atrium or 2 separate superior and inferior vena cava cannulas.

Once on CPB, the patient's temperature is cooled down to 28 degrees Celsius. Cooling and warming the patient are done with pH stat strategy, during which the carbon dioxide level is allowed to rise in the CPB circuit to maintain a normal temperature corrected pH. All patients receive inhaled NO through the endotracheal tube after weaning from CPB.

Research procedures

The subjects will be randomized by the research perfusionist to either groups of the study. Only the perfusionist will be aware of the randomization process and NO delivery. The surgeon will be blinded to group assignment. Group 1 (treatment group) will receive NO via the CPB for the duration of surgery. Once the patient is off CPB, NO administration via CPB will be discontinued and switched to endotracheal tube administration. Group 2 (control group) will be treated with a strategy identical to that in the treatment group, with the exception that they will not receive NO via CPB.

For subjects in Group 1, NO will be delivered using the Inovent Transport delivery device (Ikaria, Hampton, NJ) after calibrating the machine according to the manufacturer's instruction. While setting up and priming the CPB circuit, the NO delivery tubing will be incorporated into the oxygenator inlet gas tubing using special reducing connectors. NO sampling will be performed by adding a luer lock connector to the inlet gas tubing proximal to the oxygenator and attaching the sampling line to it.

Once CPB is initiated, NO delivery will be started at 40ppm as measured by the sampling line, and maintained at 40ppm during the procedure unless the serum methemoglobin level increases above 3%. Once the patient is off CPB, NO delivery will be discontinued, and the subject will be managed similar to controls.

Post-surgical care

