After finishing surgery, all subjects will recover in the Pediatric Surgical Heart Unit (PSHU) under the direct care of the pediatric cardiac intensivist and the surgical team. Neither physician nor nurse involved in the post-operative care will be aware of the subject's randomization assignment.

Data collection (see schedule of events below)

All patients will have the following pre-operative labs drawn before surgery as part of our standard of care: complete blood count (CBC), complete metabolic panel, coagulation profile, and blood type and cross match.

On the day of surgery, the following research related markers will be drawn in the operating room after the patient is under anesthesia and after insertion of arterial and central venous access (Time 0): cardiac troponin I, NT pro-BNP, plasma (MDA) level, superoxide dismutase, IL-6, IL-8, lactate dehydrogenase (LDH), procalcitonin, TNF alpha, CRP and CPK-MB. These markers will be rechecked at the end of CPB and before modified ultrafiltration (Time 1), after modified ultrafiltration (Time 2), 12 hours (+/- one hour) after CPB (Time 3) and 24 hours (+/- one hour) after CPB (in the PSHU) (Time 4). The amount of blood needed for each research blood draw will be 2 ml for a total of 10 ml of blood to be drawn for research purposes.

All patients will have an echocardiogram, chest radiography and the following blood tests drawn in the PSHU on a daily basis that includes: complete blood count (CBC), complete metabolic panel with kidney function and liver function tests, and coagulation profile. These tests are conducted as part of our standard of care.

All standard of care laboratory tests will be performed and billed in accordance with usual hospital procedures. All research only labs will be shipped in batch to Immunetech labs and processed according to the appropriate procedures.

Clinical data that will be collected will include: CPB time and aortic cross clamp time, fluid requirements, diuretic requirement inotropic support, ventilator hours, need to leave sternum open, ICU LOS and total hospital LOS, transfusions, blood and coagulation

factors, total amount of chest tube drainage, post-operative complications like bleeding, infection or seizures, renal dysfunction, arrhythmias, and post-operative need for extracorporeal membrane oxygenation (ECMO) support.

Schedule of Events

SOC=standard of care, MUF = modified ultrafiltration

11) Data and Specimen Banking

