The data will be collected and saved on a password-protected Excel data sheet which will be stored on the password-protected computer of principal investigator.

12) Data Management

Sample Size Estimation

Sample size estimation was calculated using PASS 12 (15) based on the number of subjects needed to compare the difference in fluid balance as measured by the total amount of fluid administered in the first 24 and 48 hours for the two groups. Power analysis was run based on published data that showed a difference 130 mL between similar group assignments. (14) A sample size of 12 achieves 83% power to detect a mean difference of 75 mL with an estimated standard deviation of 60 mL and with a significance level (alpha) of 0.05 using a two sample t-test.

Data Management

Standard of care lab values and clinical indicators as identified in protocol Section 9 will be recorded in the electronic medical record (EMR) per routine hospital procedure. Lab values of markers being collected for research only will be received in a report directly from the labs. Investigators will extract study data from the EMR or lab results onto a source document for data collection and record into an electronic spreadsheet.

Statistical Analysis Plan

Data analysis will include measures of central tendency for all demographic and outcome variables. The primary endpoint of clinical indicators, including fluid balance, inotropic support, ventilator hours, and LOS will be compared between groups using a Repeated Measures ANOVA with post hoc comparisons, Student's t-test or chi-square as appropriate. A p-value less than, or equal to, 0.05 will be regarded statistically significant.

Secondary outcomes to be compared between groups include the biochemical markers. Analysis will be done using Student's t-test and a p-value less than, or equal to, 0.05 will be regarded statistically significant.

The other indicators, number of adverse events (as determined by methemoglobin) will also be described and reported as indicated in protocol Section 13. Differences in adverse event rates will be evaluated using descriptive and inferential statistics as appropriate.

Data Storage

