 - [name], MA - Clinical Coordinator, Pediatrics and Pediatric Critical Care, Advocate Children's Hospital-Oak Lawn

- [name] – Pediatric Pulmonologist, Torero Pulmonary Specialists, S.C.

14) Withdrawal of Subjects

The FISH test to test for chromosomal abnormality is done routinely on all neonates with cardiac disease. If the FISH test result is abnormal after the Norwood procedure is performed, indicating genetic syndromes, the subject will be withdrawn from the study.

It may be possible that RV wall and endocardial fibroelastosis may not be evident on the pre-operative echo but that it would be identified during the operation. If this condition is identified during the operation, the subject will be withdrawn at that time, randomization will be unblended and the subject will be treated as if they are not in the study (e.g. will not have extra study blood drawn).

At any time, the attending physician can withdraw a patient from this study if they feel it is warranted based on clinical condition. Parents will be notified by the attending physician. The parents have the right to withdraw their child from the study at any time. If the parent decides to withdraw their child from the study, they will be asked if medical record collection can continue until the end of hospitalization. Documentation of the conversation and their decision will be entered into the research chart and medical record.

15) Risks to Subjects

We have been using *inhaled* NO during and after surgery at our center for over 8 years. The direct risk of using NO in the CPB circuit during surgery is related to elevated methemoglobin serum level. An elevated methemoglobin level is usually treated effectively by decreasing the rate of NO administration. All surgical staff and team members are familiar with NO use.

NO administration via the cardiopulmonary bypass circuit will be monitored by checking frequent methemoglobin levels. Per our standard practice, this level is checked with every arterial blood gas which is usually performed every 30 minutes while the patient is on cardiopulmonary bypass. If the methemoglobin level increases to 3%, NO administration will be decreased until methemoglobin falls below this level. No other research-related risks are anticipated.

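### Eleven secondary markers, each drawn before and four times after NO starts, are tested only by Student's t-test at 0.05, with no time or summary fixed, no multiplicity rule and no stated role for Time 0

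*Combined protocol and SAP*

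**What the plan says.** Section 9 makes the markers the secondary endpoints: "The secondary study endpoints are to evaluate whether NO delivered through the neonatal CPB circuit can decrease various biochemical markers". It names no time point. It has ten entries because the interleukins are grouped; section 10 (Data collection) names IL-6 and IL-8 separately, which makes 11.

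Section 10 sets five draws:
- Time 0 is taken "after the patient is under anesthesia and after insertion of arterial and central venous access (Time 0").
- Time 1: "These markers will be rechecked at the end of CPB and before modified ultrafiltration (Time 1").
- Time 2 follows modified ultrafiltration.
- Times 3 and 4: "12 hours (+/- one hour) after CPB (Time 3) and 24 hours (+/- one hour) after CPB (in the PSHU) (Time 4").

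The blood volume agrees: 10 ml in total at 2 ml per draw is five draws. Study NO begins only on bypass ("Once CPB is initiated, NO delivery will be started at 40ppm"), so Time 0 is a true pre-treatment value.

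The whole inferential plan for the markers is one sentence in section 12 (Statistical Analysis Plan): "Analysis will be done using Student's t-test and a p-value less than, or equal to, 0.05 will be regarded statistically significant". Repeated Measures ANOVA appears in the same section, but only in the sentence on the primary clinical indicators.

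**The concern.** A t-test compares one number per subject between two groups. With four values per marker after treatment starts, the plan must say which number that is, and it does not. One test per marker, a test at every later time, and a time chosen per marker after seeing the results all fit the text, and in each case any p-value at or below 0.05 would be called significant.

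The markers carry Specific Aim 2, the mechanistic claim. A reader of the final report could not tell a pre-specified marker result from the best of several times or several markers. Separately, the trial pays for a baseline measurement of every marker and states no analytic use for it.

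**Working it through.** **The plan's own figure.** The only design calculation is for fluid balance: 12 per arm, difference 75 mL, SD 60 mL, alpha 0.05, two-sample t-test, 83% power. Standardised effect d = 75/60 = 1.25; noncentrality 1.25 x sqrt(12/2) = 3.06 on 22 df; two-sided power 83.3%. It reproduces, and it reproduces as a two-sided test (one-sided would be 90.7%), so two-sided 0.05 is used below. No such calculation is given for any marker.

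**False positives if NO affects no marker**

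Inputs from section 10: 11 markers, four later times. Input from section 12: 0.05 per test.

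| Reading of the text | Tests | Expected false positives | Chance of at least one, if independent |
|---|---|---|---|
| One test per marker | 11 | 11 x 0.05 = 0.55 | 1 - 0.95^11 = 43.1% |
| Every later time | 44 | 44 x 0.05 = 2.2 | 1 - 0.95^44 = 89.5% |
| One marker, best of four times | 4 | 4 x 0.05 = 0.2 | 1 - 0.95^4 = 18.5% |

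The expected counts hold whatever the correlation; the last column does not. The documents give no correlations, so three assumed pairs were simulated under the null (60,000 trials, 12 per arm, normal data):

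| Correlation between times / between markers | Any of 11 | Any of 44 | One marker, any of four times |
|---|---|---|---|
| 0.5 / 0.3 | 38.0% | 79.8% | 15.7% |
| 0.7 / 0.5 | 31.0% | 63.7% | 13.3% |
| 0.7 / 0.7 | 23.1% | 50.7% | 13.3% |

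**What Time 0 could add**

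Assume 12 complete subjects per arm (N = 24), a 1.0 SD effect and normal data. The t-test has noncentrality 1.0 x sqrt(6) = 2.449 on 22 df, power 64.9%. For ANCOVA with correlation rho between Time 0 and the later value, the variance is multiplied by (1 - rho^2) x (N - 3)/(N - 4) = (1 - rho^2) x 21/20, on 21 df:

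| rho (assumed) | Noncentrality | ANCOVA power | Against t-test, 64.9% |
|---|---|---|---|
| 0 | 2.390 | 62.6% | -2.3 points |
| 0.3 | 2.506 | 66.6% | +1.7 |
| 0.5 | 2.760 | 74.9% | +10.0 |
| 0.7 | 3.347 | 89.1% | +24.2 |

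Break-even is at rho of about 0.23.

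**Price of formal control.** Holm's first step over 11 tests uses 0.05/11 = 0.0045. For the same 1.0 SD effect, power there is 27.2% for the t-test and 28.5%, 36.8% and 57.5% for ANCOVA at rho 0.3, 0.5 and 0.7.

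**Named time or average?** Take rho 0.3 with every time and correlation 0.7 between times. The average of the four times, adjusted for Time 0, has variance ((1 + 3 x 0.7)/4 - 0.3^2) x 21/20. A time named without knowing where the effect lies has power (k/4) x 66.6% + (1 - k/4) x 5% when the effect is present at k of the four times.

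| Times with a 1.0 SD effect (k) | Average of four | Time named blindly |
|---|---|---|
| 1 | 10.6% | 20.4% |
| 2 | 28.1% | 35.8% |
| 3 | 54.2% | 51.2% |
| 4 | 78.6% | 66.6% |

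Neither choice dominates.

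**The case against.** The strongest reply is that these are secondary endpoints in a 24-subject, single-centre study. Each t-test compares randomised groups and is valid, and many trials leave secondary endpoints uncorrected. That stands, and it limits the point to how marker results may be described. It does not excuse calling every result at 0.05 significant when the tested quantity is not fixed.

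A reader might infer that the plan will run 44 tests with a near-90% chance of a false claim, or will pick the best time. The documents do not support that. The text is silent on the time, so those are upper readings, and the 89.5% also needs independent tests, which is implausible for repeated draws on the same infants. Nor does section 12 rule out a t-test on change from Time 0; the accurate statement is that no role for Time 0 is stated.

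The case for ANCOVA is also open to challenge. Its gain rests wholly on an undocumented correlation: under 2 points at 0.3 and a loss below about 0.23. A t-test at a named time would close the time-point gap by itself. This stands as a limit on the size of the benefit. Against it, the baseline is already collected, precedes study NO, and costs at most about 2 points to use.

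One could also argue against averaging over Times 1-4, because Times 1 and 2 lie on either side of ultrafiltration and "All patients receive inhaled NO through the endotracheal tube after weaning from CPB", so the effect may differ between draws. The last table shows that this does not settle the matter: the average does better when the effect spans three or four draws.

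**Conclusion.** The point holds, as one that should be corrected. The plan fixes no tested quantity for 11 markers with four later values each, and it attaches an unqualified significance label to whatever is tested. On the mildest reading, one test per marker, 0.55 false positives are expected under the null. The chance of at least one is 43% if independent, or about 23-38% at assumed between-marker correlations of 0.7 to 0.3. The figure of 2.2 is an upper limit that the text allows, not what the plan proposes.

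The primary conclusion is untouched and no single t-test is invalid. The precision argument is conditional: for a 1.0 SD effect, 65% power for the t-test against 67%, 75% and 89% for ANCOVA at assumed correlations of 0.3, 0.5 and 0.7. Marker effect size, correlations and normality are all assumptions. The missing body of the Schedule of Events does not change the reading, since section 10 gives the draw times in words.

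**What to change.** Amend section 12 before unblinding:

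1. For each marker, fix one later time or one summary over times. A named time and an average are both acceptable; what matters is that the choice precedes the data.
2. Analyse it by ANCOVA adjusted for that marker's Time 0 value, and report the difference with a 95% CI.
3. Either label the markers exploratory and remove the significance wording, or keep significance claims and apply Holm or false-discovery-rate control across the 11 tests.
4. Show the remaining times descriptively.

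The cost is wording only: no extra blood or subjects. There are four downsides. ANCOVA loses about 2 power points with 12 per arm if the Time 0 correlation is near zero. Any single time or summary can miss an effect confined to other draws. The exploratory label limits what is claimed but leaves the 11-test false-positive rate where it was. Holm does lower that rate, but at its first step power per marker for a 1.0 SD effect is only about 29-58% with ANCOVA at correlations of 0.3 to 0.7.

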PROTOCOL TITLE: Efficacy of Nitric Oxide Administration in Attenuating Ischemia / Reperfusion Injury During Neonatal Cardiopulmonary Bypass Version3_6.3.16

Title: Efficacy of Nitric Oxide Administration in Attenuating Ischemia / Reperfusion Injury During Neonatal Cardiopulmonary Bypass

NCT: 02151877

Version 3_3Jun2016

Protocol Title

Efficacy of Nitric Oxide Administration in Attenuating Ischemia / Reperfusion Injury During Neonatal Cardiopulmonary Bypass

1) IRB Review History

N/A

2) Objectives

Hypothesis: The introduction of nitric oxide (NO) directly into the cardiopulmonary bypass circuit, during neonatal surgical repair of congenital heart lesions, will attenuate ischemia reperfusion injury that can complicate the surgical procedure and postoperative recovery.

Specific Objectives: During the Norwood procedure for hypoplastic left heart syndrome (HLHS) or its variants, there is around 20 to 30 minutes of ischemia to the myocardium between cardioplegia doses, and 20 to 30 minutes of interruption of flow to the lower body during reconstruction of the aortic arch. The proposed study will help to know if NO can decrease ischemia reperfusion injury to the myocardium, as well as to the lower body organs (liver, kidney, gastro-intestinal tract).

Specific Aims:

- 1) Evaluate whether NO delivered through the neonatal CPB circuit can decrease the clinical signs of ischemia/reperfusion injury and/or cardiac dysfunction as reflected by fluid balances, inotropic support, diuretic requirement, length of ventilator support, length of ICU stay, and length of hospital stay.
- 2) Evaluate whether NO delivered through the neonatal CPB circuit can decrease various biochemical markers of ischemia/reperfusion injury and oxidative damage [cardiac troponin I, interleukins (IL), tumor necrosis factor (TNF), N-terminal prohormone for brain natriuretic peptide (NT-proBNP), lactate dehydrogenase (LDH), plasma anti-oxidant levels, plasma malondialdehyde (MDA) levels].
- 3) Evaluate the safety of NO delivered through the neonatal CPB circuit as measured by adverse events during the course of the study.

3) Background

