All information gathered during this study will be kept confidential. Subjects will be assigned case numbers and data collection forms that including the patient name will only be seen by the research team. All data collection forms will be placed in a confidential folder within the principal investigator's locked office. Tabulation of data will be stored in a password protected file within a password protected computer. The results of this study may be published in scientific journals or be presented at professional meetings, but no individuals will be identified. The collection and handling of data will be in complete accordance with the HIPPA regulations. The research-related records for this study may be inspected by a federal regulatory agency and the Institutional Review Board.

Data collected for this study will be maintained for three years after the investigation is complete and the FDA is notified.

13) Provisions to Monitor the Data to Ensure the Safety of Subjects

MONITORING PLAN

The individuals responsible for data safety and monitoring will be [name] (PI). Quality control will include regular data verification and protocol compliance checks by [name].

COLLECTION AND REPORTING OF SAEs AND AEs

Throughout the study, [name] and the study research coordinator will monitor study participants for adverse events. [name] will review all adverse events (AEs) and serious adverse events (SAEs) individually and in aggregate on a biweekly basis. [name] will report all AEs and SAEs to the Advocate Health Care IRB according to the AE reporting guidelines.

For this study, the following standard AE definitions will be used:

Adverse event: Any unfavorable and unintended sign (including an abnormal laboratory finding), symptom or disease, that did not exist at the time of the subject's entry into the study and that is temporally associated with the use of the study medication, regardless of whether it is considered related to the study medication.

Suspected adverse reaction: A suspected adverse reaction means any adverse event for which there is a reasonable possibility that the drug caused the adverse event. For the purposes of IND safety reporting, ‘reasonable possibility’ means there is evidence to suggest a causal relationship between the drug and the adverse event. A suspected adverse reaction implies a lesser degree of certainty about causality than an adverse reaction.

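### The SAP ties its adverse event count to methemoglobin, which contradicts Aim 3 and Section 13, and nothing else commits the final analysis to all AEs and SAEs

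*Combined protocol and SAP*

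**What the plan says.** Section 2, Aim 3, sets the safety objective: "Evaluate the safety of NO delivered through the neonatal CPB circuit as measured by adverse events during the course of the study".

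Section 9 names one primary safety measure, a laboratory level: "The primary safety measure is the level of methemoglobin while NO is being administered during cardiopulmonary bypass".

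Section 13 defines an adverse event broadly: "Any unfavorable and unintended sign (including an abnormal laboratory finding), symptom or disease". The event must be new since enrolment, and it counts whether or not it is thought related to the drug. Monitoring lasts for the hospital stay.

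Section 10 collects "post-operative complications like bleeding, infection or seizures, renal dysfunction, arrhythmias" and the need for ECMO, along with transfusions and chest tube drainage.

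The Statistical Analysis Plan in Section 12 has two sentences on safety. The first takes as its variable the "number of adverse events (as determined by methemoglobin", where the parenthesis closes, and refers to Section 13 for how these events are described and reported. The second says: "Differences in adverse event rates will be evaluated using descriptive and inferential statistics as appropriate".

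Section 13 also has the DSMB compare AE and SAE rates by arm at interim reviews, the first after 12 subjects and then after every further 6.

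**The concern.** The parenthetical makes a laboratory reading taken on bypass the thing that determines an adverse event. Aim 3 and Section 13 describe something much wider in type and in time. A plan that states its safety variable in two incompatible ways lets the final report follow either.

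What is at stake is whether the final comparison by arm includes the clinical harms. Bleeding is the clearest case. The Background section says that NO inhibits platelet adhesion and aggregation, and bleeding, transfusion and drainage data are all collected, yet the SAP names none of them as a safety outcome. Someone following the parenthetical could complete the planned safety analysis without tabulating them.

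A methemoglobin count would also be a weak stand-in for safety. NO is adjusted during bypass to hold methemoglobin below 3%, so the count describes a quantity that is being actively controlled. The SAP also gives no value at which a reading becomes an event.

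**Working it through.** The plan gives no figure for safety, so the check is mainly a comparison of texts.

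| Place | What is covered | Period | Role |
|---|---|---|---|
| Section 2, Aim 3 | Adverse events, no limit by type | The study (Section 8: surgery to discharge) | Objective |
| Section 9 | Methemoglobin level | While NO is given on bypass | Primary safety measure |
| Section 10, Data collection | Bleeding, infection, seizures, renal dysfunction, arrhythmias, ECMO | Post-operative | Collection |
| Section 12, SAP, first safety sentence | Adverse events determined by methemoglobin | Not stated; methemoglobin checks are described on bypass | Final analysis |
| Section 12, SAP, second safety sentence | Adverse event rates, no stated limit | Not stated | Final analysis; no event set, test or analysis set |
| Section 13, definition | Any unfavorable sign, symptom or disease | Hospital stay | Definition and monitoring |
| Section 13, DSMB reviews | AE and SAE rates by arm; fluid balance, morbidity, mortality | From 12 subjects, then every 6 | Interim |

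**Step 1. Can the parenthetical agree with Aim 3 and Section 13?** No. A methemoglobin level cannot determine whether a subject had sepsis, a seizure, an arrhythmia, ECMO or died. Section 13 treats several of these as reportable or serious events in their own right.

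**Step 2. Does the pointer to Section 13 widen the count?** Not clearly. It says how the events are described and reported. Section 13 contains the broad definition, so a wide reading is possible, but the parenthetical remains in the same sentence. The analysis that Section 13 plans is for the DSMB reviews.

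**Step 3. Does the second SAP sentence widen it?** It carries no methemoglobin limit of its own. It also names no events and directly follows the sentence that restricts them, so it permits the broad reading without requiring it.

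**Step 4. Do the DSMB reviews replace a final analysis?** The schedule gives reviews at 12, 12 + 6 = 18 and 18 + 6 = 24 subjects, so the last falls at full enrolment. The protocol still calls these analyses interim. The first is triggered by enrolment, so at the last review some subjects may not yet have been discharged.

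**Step 5. What is left out under the literal reading?** Some harms are reached through the Section 9 primary endpoints: end organ failure (BUN, creatinine, liver function tests), duration of ventilation, and ICU and hospital stay. Those not named in any final comparison are SAEs as a class, bleeding, infection, seizures, arrhythmias, ECMO and death.

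**Step 6. What could a full comparison show with 12 per arm?** For *k* events against none, the two-sided Fisher p-value is 2·C(12,*k*)/C(24,*k*).

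- *k* = 4: 2 × 495/10,626 = 0.093
- *k* = 5: 2 × 792/42,504 = 0.037

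At least 5/12 against 0/12 is therefore needed for p ≤ 0.05. The documents give no event rates. Under assumed rates, exact power is 4.1% for 5% v 20%, 9.5% for 10% v 30% and 42.5% for 10% v 50%. This supports a descriptive table with intervals, not a set of tests.

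**Step 7. Is any design figure affected?** No. The plan's one power statement concerns fluid balance. With 12 per arm, a difference of 75 mL, SD 60 mL and a two-sided alpha of 0.05 (sidedness is not stated), the noncentrality is 75/(60·√(2/12)) = 3.06 on 22 df. Power is 83.3%, which matches the stated 83%. The change proposed here leaves it alone.

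**The case against.** The best defence is that the parenthetical is loose wording in a plan that otherwise treats safety broadly. The SAP's sentence on comparing groups has no methemoglobin limit. Section 13, to which the SAP points, holds the broad definition, severity and attribution scales, and a commitment to compare AE and SAE rates by arm. All AEs and SAEs are reviewed in aggregate every two weeks, and DSMB reports go to the principal investigator and the IRB. Several harms bear on primary endpoints. With 12 per arm, safety would be descriptive on any reading.

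Most of this stands, and it rules out stronger statements. A reader might infer that the final analysis counts methemoglobin events only, that the trial cannot answer Aim 3, or that nearly every harm is left out. The documents do not support these. The word only does not appear, the second SAP sentence allows a broad analysis, the data are collected, and an all-AE comparison by arm is planned for the DSMB.

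A reader might also assume that controls would have almost no methemoglobin events. The documents give no control rate. They say the level is checked with every arterial blood gas on bypass as standard practice, so controls may well have readings.

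The defence does not remove the contradiction. The parenthetical is a stated rule in the analysis plan, and no other sentence overrides it for the final analysis.

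**Conclusion.** Wrong as written: an internal contradiction in the safety analysis. The SAP's description of its safety variable conflicts with Aim 3 and with the Section 13 definition, and the final analysis of all AEs, SAEs and listed complications is not committed to anywhere.

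The size is best given as scope: on the literal reading, SAEs as a class and the six harms listed in Step 5 drop out of the final safety count. This rests on reading the parenthetical as it stands and on taking the DSMB comparison as interim, as the protocol labels it. If the sponsor intended the broad reading, the defect is one of wording, but the wording still has to change for the plan to say so.

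A reader might want to size the problem by the exact upper limit for no events in 12 treated subjects, 1 − 0.025^(1/12) = 26.5%. That limit applies to any outcome with a zero count at this sample size and would be the same after the correction. It does not measure this defect.

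**What to change.** In the Statistical Analysis Plan in Section 12:

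1. Delete the parenthetical that ties adverse events to methemoglobin.
2. State that the number and proportion of subjects with any AE, any SAE, death and each complication listed in Section 10, from surgery through discharge, will be tabulated by randomised arm. Give exact confidence intervals and label the table descriptive because there are 12 subjects per arm.
3. Report methemoglobin levels on bypass separately, as the primary safety measure named in Section 9. If readings are also to be counted as events, state the value that defines one.

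The cost is a few lines of SAP wording and one table from data already collected. Sample size, power, trial procedures and the DSMB schedule do not change.
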